## 6.5 Strategies to improve adherence

1. The PI will sensitize the subject to the importance of correctly applying the PI to achieve the study objectives.
2. Direct questioning by the IP regarding the application of the PI.
3. Delivery of a printed calendar specifying the date of the visit and its activities.
4. Training in completing and reviewing the "Subject Diary."
5. If deemed necessary, text messages may be sent as reminders. The content of these messages must be approved in advance by the IEC.

## 7. Methods and procedures of the study

---

### 7.1 From the research center

This study will be conducted at research centers previously evaluated by the sponsor. These centers will be institutions or establishments that conduct health research and comply with current regulations.

The research center will be responsible for forming a multidisciplinary research team to execute the clinical study according to the protocol. It is its prerogative to design the organization and select the personnel who will perform these functions. However, the sponsor requires that the Principal Investigator (PI) be a physician specialized in ophthalmology.

Any person assigned responsibility for part of the study monitoring (coinvestigator, sub-investigator, nurse, etc.) or a specific role in the study (pharmacist, administrative assistant, study coordinator, etc.) must be listed in the "Delegation of Responsibilities."

The competency and training of all individuals directly involved in study activities must be verified prior to the conduct of any protocol-related activities. This must be recorded, and documents constituting evidence of this competency and/or training must be retained in the study master file. The competency and training of personnel involved in the study, both at the central level and at the study sites, is the responsibility of the sponsor.

The sponsor must ensure that all study center personnel participating in the study are adequately trained in the study (research protocol, investigator's manual, amendments, standard operating procedures, etc.) and in ICH Good Clinical Practices prior to the start of their participation in the study. Training must be documented in writing and filed in the study's master file.

### 7.2 Clinical study registration

This clinical study will be registered by the sponsor in public clinical trial registries prior to its initiation (enrollment of the first patient): the National Registry of Clinical Trials (RNEC) of the Federal Commission for the Protection against Sanitary Risks (COFEPRIS) and on a WHO primary registry platform. WHO primary registries meet specific criteria regarding content, quality and validity, accessibility, unique identification, technical capacity, and administration. WHO primary registries meet the requirements of the International Committee of Medical Journal Editors (ICMJE).

### 7.3 Randomization and blinding

Subject randomization will be performed using a computerized allocation system. After signing the FCI, the patient will receive a patient number, which will be used to pseudonymize all information during collection and completely anonymize it during analysis.

The generation will be carried out by a third party authorized by Laboratorios Sophia, SA de CV, through its electronic system. The information corresponding to this third party will be found in the file.

Blinding will be performed by the subject, PI, and subinvestigator. Furthermore, the statistical analysis will be performed blinded for the final analysis. Blinding cannot be guaranteed for the subject.

Masking will be done through primary and secondary packaging.

They will be identified by identical labels. These, in compliance with current and applicable regulations, must contain at least:

- Name, address and telephone number of the sponsor.
- Pharmaceutical form and route of administration.
- Batch number.
- Legend "Exclusively for clinical studies"
- Expiration date.

### 7.3.1 Opening of the cecum

The cecum may be opened in the following cases:

1. Presence of a serious adverse event.
2. Safety alert for the use of the drugs under study.
3. In the event that the sponsor determines it for any security reason or other reason that it deems appropriate.
4. In the event that the regulatory authority or the ethics committee justifiably requests it and deems it necessary

## 7.4 Outcome variables

### 7.4.1 Primary outcome variables

- OSDI Test Score (TE: Day 29)
- Incidence of unexpected AEs related to the PI (TE: day 8 and 29)

### 7.4.2 Secondary outcome variables

- Changes in BCVA (TE: day 8 and 29)
- Changes in TRPL with fluorescein (TE: day 8 and 29)
- Corneal fluorescein staining changes (TE: day 8 and 29)
- Conjunctival staining changes with lissamine green (TE: day 8 and 29)
- Incidence of expected AEs (TE day 8 and 29)

### 7.4.3 Exploratory outcome variable

- Average number of applications performed daily

## 7.4.4 Definition of variables, methods and scales to be used for measurement

Variable	Guy	Unit (symbol)	Measurement method	Normal value	Evaluation time	Statistical test
Primary outcome						
OSDI	Discreet	Points (-)	Questionnaire	< 13	VB and VF	Mann-Whitney U
Unexpected EAs related to PI	Discreet	Number of cases (n)	Counting	0	VB, V1 and VF	Mann-Whitney U
Unexpected AEs related to the PI (bis)	Nominal categorical	Present/absent (-)	Observation	Absent	VB, V1 and VF	$\chi^2$ or Fisher's exact test
Of secondary outcome						
MAVC	Discreet	Fraction (-)	Snellen chart	1	VB, V1 and VF	Mann-Whitney U
TRPL with fluorescein	Continue	Seconds (s)	Direct observation with slit lamp and blue filter	>10s	VB, V1 and VF	Mann-Whitney U
Corneal staining with fluorescein	Ordinal	Degrees (-)	Direct observation with a slit lamp on the Oxford scale	0	VB, V1 and VF	$\chi^2$ or Fisher's exact test
Conjunctival staining with lissamine green	Ordinal	Degrees (-)	Direct observation with slit lamp and cobalt blue filter, Oxford scale graduation	0	VB, V1 and VF	$\chi^2$ or Fisher's exact test
EA	Discreet	Number of cases (n)	Counting	0	VB, V1 and VF	Mann-Whitney U
EA (repeat)	Nominal categorical	Present/absent (-)	Observation	Absent	VB, V1 and VF	$\chi^2$ or Fisher's exact
Exploratory						
Number of applications made daily	Discreet	Number of applications (n)	Count by Subject's Diary	>4	V1 and VF	Mann-Whitney U

**Table 2**Operational definition of variables

The variables, method, and scales for their measurement are described in detail below. They are listed in order according to **Table 2**

**7.4.4.1 OSDI Score**

The OSDI is a validated and reliable instrument for measuring dry eye severity. It has the psychometric properties necessary for use as an outcome variable in clinical studies. [40]It consists of a 3-question, 12-item questionnaire. Responses are based on frequency and offer 5 options, ranging from 4 (all the time) to 0 (none of the time). Questions 2 and 3 also contain the option NA. (See **15.1.**) The OSDI score is calculated based on the following formula:

$$OSDI = \frac{D \times 25}{E}$$

Where:

*D* = sum of the points of the questions answered

*E* = number of items answered, those answered with NA are not counted as answered

The OSDI score will be recorded on the Electronic Case Report Form (FERC)

Management as an AE: An increase of more than 40% from the baseline OSDI score should be reported and managed as an AE due to lack of efficacy.

#### *7.4.4.2 Adverse events*

As defined in section **8.2**, an EA It is any unfavorable medical occurrence in a subject to whom a PI is administered, regardless of the causal attribution.

The management of AEs will be carried out as described in the Adverse Events section.

The IP will record any AEs that the study subjects may present in the corresponding section of the FERC and will also include them in the clinical record.

For an adequate evaluation of AEs, in addition to the targeted questioning, a Comprehensive Ophthalmologic Evaluation must be performed at each visit. This evaluation consists of an ophthalmologic examination of the eyelids and adnexa, anterior segments, and posterior segments, which are performed during a routine ophthalmologic examination and are not specifically included in the study variables. The posterior pole evaluation may be performed with direct or indirect ophthalmoscopy, with or without pharmacological mydriasis, at the discretion of the PI. The fundus will be assessed for abnormalities that could alter the study results. IOP will be measured during this evaluation, using the PI's chosen instrument, and should be measured after the stain evaluation. The results of the evaluation will be recorded in the clinical record. Only findings that the PI considers to be AEs will be reported in the FERC.

The expected adverse effects associated with the use of PIs are: blurred vision, burning, eye irritation, foreign body sensation, and sticky eyelashes. They are expected to be transient, lasting no more than 30 seconds after PI instillation, and to be mild in intensity.

#### *7.4.4.3 Best Corrected Visual Acuity*

Visual acuity (VA) is a test of visual function. Spatial VA is the ability to distinguish separate elements of an object and identify them as a whole. It is quantified as the minimum angle of separation (located at the nodal point of the eye) between two objects that allows them to be perceived as separate objects.

Snellen notation is described as the distance at which the test is performed divided by the distance at which the letter vertically equals 5 minutes of arc. Thus, at 6 meters, a letter 6/6 (20/20) equals 5 minutes of arc, a letter 6/12 (20/40) equals 10 minutes, and a letter 6/60 (20/200) equals 50 minutes. The Snellen fraction can also be expressed as a decimal (i.e., 20/20 = 1 and 20/40 = 0.5).

[41]

VA will be assessed at baseline, without refractive correction, using the Snellen chart. This chart will be placed in a location with adequate natural or artificial lighting and at a distance of 3 m from the subject being assessed. Visual acuity will be measured in each eye, starting with the right eye (RE), asking the subject to keep both eyes open and using an occluder to cover the left eye (LE); the subject will read aloud the lines indicated by the evaluator. The evaluator will record the smallest line of letters visible as the RE VA in the clinical record. The LE is then assessed using the same method.

The subject's objective and subjective refractive correction will then be performed. The subjective refraction result will be reported as BCVA, recorded as a fraction in the clinical record and on the FERC, and recorded as a decimal on the FERC. By definition, BCVA cannot be less than VA.

Management as AE: A decrease of more than 2 lines on the Snellen chart should be reported and managed as an AE.

#### *7.4.4.4 Tear film breakup time*

One of the first aspects of the tear film to change when there is a change in the ocular surface is its stability. In general, if the corneal or conjunctival surface is damaged, it is unlikely that a stable tear film can be maintained.

The most common method for assessing tear film stability is fluorescein-based TRPL. Once fluorescein has been instilled (see **7.4.4.5**), the patient is asked to hold their breath after blinking 1 to 2 times using the cobalt blue filter. The fluorescein-stained precorneal layer will shift to less fluorescent or nonfluorescent regions. The time elapsed from the last blink to the appearance of these regions is the TRPL. It is reported in seconds in the clinical record and on the FERC.

Management as an AE: A decrease in TRPL of more than 40% from baseline should be reported and managed as an AE due to lack of efficacy.

#### *7.4.4.5 Corneal staining with fluorescein*

A drop of topical anesthetic is instilled into the conjunctival fornix. A second drop is then applied to the tip of the fluorescein strip, allowing it to sit on the strip for 5 seconds to elute the dye, shaking off the excess at the end. A small amount of contact is made between the strip and the conjunctiva in the temporal fornix while the patient looks upward, avoiding damaging the conjunctiva. After assessing the TRPL, 4 to 8 minutes after instillation of the dye, the corneal fluorescein staining is assessed using a slit lamp with a cobalt blue filter. It is graded according to the Sjögren's Clinical Collaboration Alliance (SICCA) Ocular Staining Grading (OSG). [42]

According to the CTO, grade 0 corresponds to the absence of punctate epithelial erosions (PEEs); grade 1 is defined as the presence of 1-5 PEEs; grade 2 corresponds to 6-30 PEEs; and >30 PEEs will be classified as grade 3. An additional grading point will be added if: 1) PEEs with a diameter of 4 mm are present in the central portion of the cornea; 2) filaments are observed; and 3) confluent staining patches, including linear staining, are observed. [42] See **Figure 4**

The IP will record in the file and with the FERC the grades awarded for corneal staining of OD and OS, respectively. The maximum grade per eye is 6.

Management as AE: Corneal staining that is greater than that recorded as baseline will be considered AE due to lack of efficacy.

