#### *7.4.4.6 Conjunctival staining with lissamine green*

After the fluorescein examination, a drop of saline solution will be applied to the tip of the lissamine green strip, allowing it to sit on the strip for 5 seconds to elute the dye. A drop from the strip is instilled into the temporal fornix while the patient looks up, without damaging the conjunctiva. The patient may be asked to blink repeatedly to avoid accumulation in the conjunctival folds. The examination should be performed between 1 and 4 minutes after instillation through a neutral density filter or a red-free filter. It will be graded according to the SICCA CTO. [42]

In CTO, grade 0 is defined as the presence of 0 to 9 lissamine green staining points in the interpalpebral bulbar conjunctiva (scoring the temporal and nasal portions separately); grade 1 is defined by the presence of 10 to 32 points; grade 2 by 33 to 100; and grade 3 by >100 points. Because of the difficulty in counting individual points in a moving eye, any area  $\geq 4 \text{ mm}^2$  of confluent points is considered >100 points [42]. See **Figure 4**

[figure not shown]
The IP will record, in the file and with the FERC, the sum of the grades awarded to the temporal and nasal portions for OD and OS, respectively. The maximum grade per eye is 6.

Management as AE: Conjunctival stains that obtain scores  $\geq 3$  and that are higher than the baseline score will be considered AE due to lack of efficacy. For example: Subject X obtains a baseline score of 1, and at a follow-up visit, his staining is rated as 2. This does not need to be managed as AE. If he obtains a score of 3 or higher, he should be managed as AE.

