## 15.2 SICCA CTO format

## Formato de Calificación de Tinción Ocular del SICCA

Ficha de identificación	
No. de estudio: SOPH176-1218/I-II	Fecha: / / /
Iniciales del sujeto: 176-	No. de sujeto: 176-

OD

OS

Verde lisamina  
(solo conjuntiva)Fluoresceína  
(solo córnea)

[figure not shown]
[figure not shown]
Grado	Puntos
0	0-9
1	10-32
2	33-100
3	>100

Grado	Puntos
0	0
1	1-5
2	6-30
3	>30

Verde lisamina  
(solo conjuntiva)Fluoresceína  
(solo córnea)

Grado	Puntos
0	0-9
1	10-32
2	33-100
3	>100

Grado	Puntos
0	0
1	1-5
2	6-30
3	>30

Puntos adicionales para la tinción de fluoresceína solamente:

+1 si hay parches de tinción confluentes +1 si hay tinción en el área pupilar +1 si hay filamentos 

Puntos adicionales para la tinción de fluoresceína solamente:

+1 si hay parches de tinción confluentes +1 si hay tinción en el área pupilar +1 si hay filamentos 

Puntaje Córnea: \_\_\_\_\_

Puntaje Conjuntiva: \_\_\_\_\_

Puntaje Córnea: \_\_\_\_\_

Puntaje Conjuntiva: \_\_\_\_\_

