6.0 Analysis Plan

The variables to be considered in the protocol are described below.

Primary efficacy outcome variables:

- OSDI test score.

Secondary efficacy outcome variables:

- Changes in best corrected visual acuity (BCVA).
- Changes in corneal and conjunctival staining with lissamine green.
- Corneal and conjunctival staining changes with fluorescein.
- Changes in tear film break-up time (TRL) with fluorescein.

Security Variables

Primary Safety outcome variable:

- Incidence of unexpected adverse events (AEs) related to the drug.

Secondary safety outcome variable:

- Incidence of expected AEs.

Table 2. Operational Definition of the Variables

Variable	Definition Conceptual	Definition Operational	Scale of measurement	Category
Events adverse	Any event adverse adverse doctor that occurs in a patient or clinical research subject who was administered a collected through the pharmaceutical product and that, not necessarily has a relationship causal with this treatment.	The events adverse effects manifested during the conduct of the study will be electronic CRF.	• Nominal • Frequency: • Intensity: 0= Mild 1= Moderate 2= Severe • Causality: 0=Probably or possibly related. 1=Unlikely related.	Subjects presenting AE/Total number of exposed subjects.
Ocular Surface Disease Index Score (OSDI).	The OSDI is a questionnaire designed to establish a severity and classification of the dry eye according to its symptoms.	The evaluator will apply the questionnaire to the subject and allow him to do so answer in calm without any kind of pressure and/or coercion. See Annex 1. OSDI.	Continue	Score: $OSDI = \frac{(Suma\ del\ puntaje)25}{\# \ de \ respuestas \ contestadas}$
Changes in corrected visual acuity (BCVA).	Visual acuity corrected (BCVA) is a test of visual function. Spatial VA is the ability to distinguish separate elements of an object and identify them as a whole. It is	Booklet of Snellen	Quantitative discrete.	Fraction, normal value = 0.6 to 2.0

It quantifies the minimum angle of separation (located at the nodal point of the eye) between two objects that allows them to be perceived as separate objects.
				

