Changes of corneal and conjunctival staining with green lissamine.	Detection of epithelial defects in the conjunctiva and cornea.	Observation direct with slit lamp, Oxford scale	Qualitative Ordinal	
Degrees:
 
The staining is presented in a series of panels (AE). The staining points range from 0-5 for each panel and from 0-15 for the total exposed area of conjunctiva and cornea.

		See Annex 2.		Oxford scale.
Corneal and conjunctival staining changes with fluorescein.	Detection of epithelial defects in the conjunctiva and cornea.	Direct observation with slit lamp and cobalt blue filter, Oxford scale	Qualitative Ordinal	
Degrees:
 
The staining is presented in a series of panels (AE). The staining points range from 0-5 for each panel and from 0-15 for the total exposed area of conjunctiva and cornea.

		See Annex 2.		Oxford scale.
Changes in tear film break-up time (TRPL) with fluorescein.	The stability of the Tear film is usually evaluated clinically by the TRL. This involves instilling fluorescein on the ocular surface to allow visualization of the tear film and measure the time it takes for the tear film to break up after the last blink.	It will be measured at end of a blink and you will be asked not to blink immediately until the tear film on the cornea breaks.	Quantitative continues.	Normal: > 10 seconds.

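### Ocular staining is graded by SICCA in the protocol methods and form but by Oxford in Protocol Table 2 and the SAP, so the SAP's staining variables cannot be derived from the data collected

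*Protocol*

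**What the plan says.** **Protocol methods and form.** Section 7.4.4.5 sets the scale for corneal fluorescein staining: "It is graded according to the Sjögren's Clinical Collaboration Alliance (SICCA) Ocular Staining Grading (OSG"). The grade comes from a count of erosions plus up to three extra points: "The maximum grade per eye is 6". Section 7.4.4.6 covers conjunctival lissamine green: "It will be graded according to the SICCA CTO". Nasal and temporal grades are added, again to a maximum of 6 per eye. The annexed recording sheet (15.2) is headed "Formato de Calificación de Tinción Ocular del SICCA" and limits lissamine green to the conjunctiva and fluorescein to the cornea.

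**Protocol Table 2 (operational definitions, section 7.4.4).** Both staining rows name the Oxford scale. The lissamine green row reads "Direct observation with slit lamp and cobalt blue filter, Oxford scale graduation". Section 7.4.4.6 has the same dye read "through a neutral density filter or a red-free filter". The table keeps one dye per site and gives no numeric range.

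**SAP.** Section 6.0 lists "Changes in corneal and conjunctival staining with lissamine green" and a matching variable for fluorescein on both sites. SAP Table 2 assigns both to Oxford: "The staining points range from 0-5 for each panel and from 0-15 for the total exposed area of conjunctiva and cornea". SAP Annex 10.2 shows the Oxford panels with a single grade from 0 to V.

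**Analysis.** Protocol 10.1.2 and SAP 7.0 put qualitative variables, ordinal ones included, into 2x2 tables, with McNemar's test within groups and chi-square or Fisher's test between groups. No cut-point is given.

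**The concern.** The SAP must define variables that can be built from what the sites record. Here the protocol methods and form use one scale and one dye per site, while the SAP uses another scale and both dyes on both sites. An analyst who follows the SAP literally has no data for half of each variable and no rule for turning SICCA grades into Oxford grades. The analyst would have to redefine two secondary efficacy endpoints after the data are in, which is the discretion a SAP is meant to remove.

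There is a second, less certain risk. Both scales stand inside the protocol itself, and six centres are planned (Protocol 5.5). A centre that took its method from Protocol Table 2 would produce grades that could not be pooled with the others.

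**Working it through.** No power or sample-size calculation bears on this point. The check is to rebuild each scale's range and compare what is defined with what is recorded.

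**Step 1. Reproduce the stated maximum of 6 per eye.**
- SICCA cornea (7.4.4.5): base grade 0-3, plus one point each for central staining, filaments and confluent patches: 3 + 1 + 1 + 1 = 6.
- SICCA conjunctiva (7.4.4.6): nasal 0-3 plus temporal 0-3: 3 + 3 = 6.

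Both agree with the protocol.

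**Step 2. Rebuild the SAP range.** With 0-5 per panel, a total of 15 needs 15 / 5 = 3 exposed areas per eye. The SAP does not say how many areas are scored or which they are, so three is an assumption. The annex shows only a single 0-V grade.

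**Step 3. Set the sources side by side.**

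| Source | Scale | Fluorescein | Lissamine green | Range |
|---|---|---|---|---|
| Protocol 7.4.4.5, 7.4.4.6 | SICCA | cornea | conjunctiva | 0-6 per eye, each |
| Protocol Annex 15.2 form | SICCA | cornea only | conjunctiva only | grades 0-3; corneal extra points |
| Protocol Table 2 | Oxford | cornea | conjunctiva | none given |
| SAP 6.0, SAP Table 2 | Oxford | cornea and conjunctiva | cornea and conjunctiva | 0-15 |
| SAP Annex 10.2 | Oxford | not stated | not stated | 0-V |

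**Step 4. Can the SAP variables be derived?** Each SAP variable needs one dye on two sites, so two dyes give 2 x 2 = 4 dye-by-site scores. The form records 2 of the 4. Corneal lissamine green and conjunctival fluorescein are missing. The 2 that exist are on a different scale: SICCA grades come from dot counts and extra points, Oxford grades from matching a panel. The documents offer no conversion. Neither SAP variable can be computed.

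**Step 5. Can the protocol endpoints be analysed?** Protocol 7.4.2 lists corneal fluorescein and conjunctival lissamine green. Both are on the form, so both can be analysed on SICCA grades.

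**Step 6. What does the 2x2 plan still lack?** A 0-6 score can be split in 6 places, a 0-5 grade in 5 and a 0-15 total in 15. No split is named, so the planned test is not fully specified on any of the scales.

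**Step 7. How did the SAP diverge?** SAP 8.0 lists the parts changed to match the current protocol: sections 2.0, 3.0, 5.0 and 7.0 and Table 1. Section 6.0, which holds these definitions, is not listed.

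**The case against.** The strongest reply is that data collection is in practice unambiguous. Protocol 7.4.4 says its table is expanded in the sections that follow. The visit lists in 7.5.1 send the investigator to 7.4.4.5 and 7.4.4.6, and the only staining form annexed to the protocol is SICCA. The Oxford panels are annexed only to the SAP. The entry counts also fit SICCA: more than 5 corneal sites starts at grade 2 (6-30) and more than 9 conjunctival sites at grade 1 (10-32). On this view Protocol Table 2 carries a wrong label and the cobalt blue filter may have slipped from the fluorescein row.

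Most of this stands, and it sets the limits of the point. It does not rescue the SAP: the clearer it is that sites record SICCA, the clearer it is that the SAP variables have no data behind them.

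Four stronger readings might be inferred, and the documents do not support them:
- *The staining endpoints cannot be analysed at all.* Only the SAP's versions cannot; step 5 covers the protocol's own.
- *Centres will mix scales.* This is possible, because Protocol Table 2 is part of the protocol, but the operative instructions and form point one way.
- *Protocol Table 2 also prescribes 0-15 with both dyes on both sites.* That appears only in the SAP. Nor is 0-6 against 0-15 a like-for-like comparison: 6 is one site, while 15 covers cornea plus conjunctiva. The two SICCA site scores sum to 12 per eye.
- *The safety decision is compromised, because staining rises can be reported as adverse events.* Those thresholds stand in the same sections that set SICCA, and the documents do not say that such events would count as unexpected and related. No effect on the safety rule is shown.

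**Conclusion.** The plan is wrong as written. The protocol methods and form contradict Protocol Table 2 on the scale and on the lissamine green filter. They contradict the SAP on the scale and on which dye is scored where. The consequence that can be shown is specific: both SAP staining variables are underivable. The protocol plans staining assessments at days 8 and 29, so both post-baseline time points are affected.

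The conclusion assumes that the annexed form is the only staining source record. The electronic case report form itself is not in the documents, but 7.4.4.5 and 7.4.4.6 describe the grades entered there as the same SICCA scores. Protocol 7.6.2 requires entries to be transcribed from source, so extra electronic fields would have nothing behind them.

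This should be corrected before sites are trained. It does not threaten the trial's main conclusion.

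**What to change.** 1. **One scale and one dye per site.** In Protocol Table 2, the SAP 6.0 variable list, SAP Table 2 and SAP Annex 10.2, replace the Oxford definitions with what the form records: SICCA corneal fluorescein, 0-6 per eye, and SICCA conjunctival lissamine green, nasal plus temporal, 0-6 per eye.
2. **Delete** the corneal lissamine green and conjunctival fluorescein variables from the SAP.
3. **Filter.** Reconcile Protocol Table 2 with 7.4.4.6 so that a single statement remains for lissamine green.
4. **Analysis.** Relabelling alone leaves the 2x2 tables undefined. Either analyse the 0-6 score as ordinal, for example with a rank test between groups (the plan already names Mann-Whitney for other variables), or state the cut-point in advance in both documents.
5. **Change record.** Add section 6.0 to the list in SAP 8.0.

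The cost is wording in the protocol table and three parts of the SAP, plus a sentence or two on the analysis. The protocol edit goes through the amendment route in Protocol 11.2. No extra subjects, visits or measurements are needed. If any centre has already graded subjects, confirm from its source forms which scale it used, because the documents give no way to convert Oxford grades afterwards.
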